10.1 EFFECTIVENESS ANALYSES

The effectiveness analyses will be based on the evaluable population. Baseline is defined as the last non-missing assessment before the first cycle of treatment.

In addition to the entire evaluable population, summaries will be provided for the following cohorts:

- Participants with 1 treatment session
- Participants with 2 treatment sessions

Some effectiveness parameters are also measured or reported at 8 weeks post treatment session #1. Descriptive summaries will be provided for this visit similar as for the effectiveness endpoints at the final visit.

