10.2 PRIMARY ANALYSIS

The primary endpoint of the study will be the overall participant satisfaction based on CSQ Item question #1 at 12 weeks after the final treatment (measured at week 12 for participants who received 1 treatment session, week 20 for 2 treatment sessions) for non-invasive fat reduction in CoolSculpting participants, including participants who receive treatment in the abdomen alone, flanks alone, or both abdomen and flanks.

The CSQ consists of 3 versions: CSQ-Abdomen, CSQ-Flank, CSQ-Abdomen and Flank; Participants with abdomen only treatment will be administered only the CSQ-Abdomen. Participants with flank only treatment will be administered only the CSQ-Flank version. Participants with both abdomen and flank treatments will be administered all 3 versions (CSQ-Abdomen, CSQ-Flank, and CSQ-Abdomen and Flank)); however, only CSQ-Abdomen and Flank will be used for the primary analysis. In each version, the CSQ Item question #1 is “Rate your overall satisfaction with the fat reduction procedure on the treated area”, with the following categories:

- Very satisfied
- Satisfied
- Neither satisfied nor dissatisfied
- Dissatisfied
- Very dissatisfied

‘Very satisfied’ and ‘Satisfied’ will be categorized as a new category, ‘Satisfied’.

The number and percentage of participants will be presented by category at 12 weeks after the final treatment, regardless of the CSQ version.

Furthermore, the 95% confidence interval on the proportion by category at 12 weeks after the final treatment, regardless of the CSQ version will be calculated using normal approximation method.

10.3 **SECONDARY ANALYSES**

All secondary endpoints will be measured at Week 12 for participants who received 1 treatment session and at Week 20 for participants who received 2 treatment sessions. The following analyses will be provided:

- Proportion of participants by treated area(s) (abdomen, flanks, and both abdomen and flanks) with “satisfied” or “very satisfied” on the CSQ Item #1.
- Proportion of participants by number of treatment cycles who received 1 or 2 treatment sessions with “satisfied” or “very satisfied” on CSQ Item #1.
- Proportion of participants with “Satisfied” or “Very Satisfied” on CSQ Item #1 by BMI categories (18.5 - < 25, 25 - ≤ 30)
- Mean change in volume of fat from baseline as measured by 3D photography.

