17.2 VISIT TIME WINDOWS

The analysis visit windows for effectiveness endpoints will be defined as follows

Error! Reference source not found. Effectiveness Analysis Visit Definitions

Analysis Phase	Analysis Visit (Derived)	Scheduled Study Visit (eCRF)	Window
Pretreatment	Baseline	Visit 2	Last assessment for which the assessment date is less than the treatment start date
Treatment	Final treatment	The final evaluations will be done on or +14 days of week 12 for participants who receive 1 treatment session; on or +14 days of week 20 for participants who receive 2 treatment sessions	Latest non-missing assessment after treatment start date

If the assessment date (or visit date, if the assessment date is unavailable) is on or after the date of the first study treatment, the study day is calculated as: assessment date – date of the first study treatment + 1. If the assessment date (or visit date, if the assessment date is unavailable) is before the date of the first study treatment, the study day is calculated as: assessment date – date of the first study treatment. Therefore, a negative day indicates a day before the start of the study intervention.

If multiple assessments were taken within an analysis window, the assessment obtained on the day closest to the target day will be used; in the case of a tie, the assessment obtained on the later day will be used in the analysis.

17.317.4**MISSING DATE OF THE LAST STUDY TREATMENT**

When the date of the last study treatment is missing for a participant in the Safety Population, all efforts should be made to obtain the date from the Investigator. If after all efforts are made it is still missing, the last available treatment record date will be used as the last treatment date.

17.5**MISSING SEVERITY ASSESSMENT FOR ADVERSE EVENTS**

If severity is missing for an AE that started before the date of the first study treatment, an intensity of mild will be assigned. If severity is missing for an AE that started on or after the date of the first study treatment, an intensity of severe will be assigned. The imputed values for severity assessment will be used for the incidence summary; the values will be shown as missing in the data listings.

17.6**MISSING CAUSAL RELATIONSHIP TO STUDY TREATMENT FOR ADVERSE EVENTS**

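### SAP 17.2 takes the latest value after treatment start as final: this ignores the Week 12/20 timing, conflicts with its own closest-to-target rule, and could let an early 3D volume stand as final

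*SAP*

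**What the plan says.** The table in SAP 17.2, as visible, derives two effectiveness visits, baseline and final. For the final visit the window is the "Latest non-missing assessment after treatment start date". The neighbouring cell in that row gives the scheduled timing: Week 12 for one session and, for two sessions, "on or +14 days of week 20 for participants who receive 2 treatment sessions". Below the table, when several assessments fall in one window, "the assessment obtained on the day closest to the target day will be used". No target day is given as a number.

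The timing of the endpoints is fixed elsewhere. SAP 10.3 states: "All secondary endpoints will be measured at Week 12 for participants who received 1 treatment session", and Week 20 applies after two sessions. Protocol 6.2 says the same and exempts only adverse events. SAP 18.0 declares no change from the protocol.

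SAP 10.1 notes that some effectiveness parameters are also recorded at Week 8 and adds: "Descriptive summaries will be provided for this visit similar as for the effectiveness endpoints at the final visit". It also asks for separate summaries of "Participants with 2 treatment sessions". SAP 6.3 admits a participant to the evaluable population only if CSQ Item #1 is reported 12 weeks after the final treatment.

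The two baseline definitions differ. SAP 10.1 has: "Baseline is defined as the last non-missing assessment before the first cycle of treatment". SAP 17.2 has: "Last assessment for which the assessment date is less than the treatment start date".

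**The concern.** The window opens at the first treatment and has no lower or upper day. Followed literally, it admits any post-treatment record as the final one, including a Week 8 record and, in a two-session participant, one taken before the second session. It also names a selection rule (latest) that differs from the rule printed below the same table (closest to target).

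Two things are at stake. First, where an assessment is repeated, the SAP does not determine which record is analysed, so the choice would be made outside the plan in an open-label study. Second, mean change in fat volume could be reported as the result 12 weeks after the last session while including values from well before that point.

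**Working it through.** **1. The two rules side by side.** SAP 17.2 counts study day as assessment date minus first treatment date plus 1. Week 8 is 56 + 1 = Day 57, Week 12 is 84 + 1 = Day 85, and Week 20 is 140 + 1 = Day 141. Adding 14 days gives scheduled ranges of Days 85 to 99 and Days 141 to 155. The assessment days below are examples.

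| Participant | Records on | Latest | Closest to target |
|---|---|---|---|
| One session | Days 57, 85 | 85 | 85 |
| One session | Days 85, 99 | 99 | 85 |
| One session | Days 85, 110 | 110 | 85 |
| One session | Day 57 only | 57 | 57 (no choice to make) |
| Two sessions | Day 57 only | 57 | 57 (no choice to make) |

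With a single on-schedule final record the rules agree. They part when there is a repeat. The second row lies wholly inside the scheduled range, so reading the scheduled-visit cell as a bound does not remove that conflict. It would remove the third row and the last two. In the last two rows the only record is 28 days before the Week 12 target (85 − 57) or 84 days before the Week 20 target (141 − 57), and the closest-to-target rule cannot reject it.

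**2. Which endpoints are exposed.**

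- *Repeat records:* CSQ and 3D volume alike, since SAP 17.2 covers all effectiveness endpoints.
- *Early record used as final, CSQ Item #1:* not exposed if SAP 6.3 is applied as written. A participant with only a Week 8 answer is not evaluable.
- *Early record used as final, 3D volume:* exposed. SAP 6.3 screens on CSQ Item #1 alone, so a participant can be evaluable without a final image.

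**3. Size for 3D volume.** The plan gives no figure on this point. Let n be the evaluable number, k the number without a final image whose earlier image is used, and r the ratio of early to final change. If those k would have had the same mean final change M as the rest:

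reported mean = [(n − k)M + k·r·M]/n = M[1 − (k/n)(1 − r)],

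so the relative understatement is (k/n)(1 − r).

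- n = 98 is the sample size in SAP 15.0 before the dropout allowance.
- k is assumed; the documents give no rate of missing images.
- r is assumed. The only time course in the documents is in protocol 5.1.2: a fat-layer reduction of 20.4% at 2 months and 25.5% at 6 months, so 20.4/25.5 = 0.80. That is ultrasound thickness after one treatment with a prototype device in 9 subjects, so it is illustrative only.

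| k of 98 | r = 0.8 | r = 0.5 | r = 0 (early image shows no change) |
|---|---|---|---|
| 2 | 0.41% | 1.02% | 2.04% |
| 5 | 1.02% | 2.55% | 5.10% |
| 10 | 2.04% | 5.10% | 10.20% |

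The same k weighs more in the two-session cohort. With an assumed cohort of 49, k = 5 and r = 0.8 give (5/49)(0.2) = 2.04%. If no image is taken between the first session and the final visit, k = 0 and the understatement is zero.

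**The case against.** The strongest reply is that the sections, read together, leave little doubt about intent. The final row names one record, so the general sentence below the table has nothing left to select. SAP 10.1 treats Week 8 as a visit distinct from the final one, and SAP 10.3 and protocol 6.2 fix the secondary endpoints at Week 12 or 20. Only one final visit is planned, so a repeat image would be unusual. Volume is a descriptive secondary endpoint in a study that tests no hypothesis.

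Much of this stands. The intent is clear, and the two rules differ only for repeats. But SAP 17.2 is the section from which the analysis value is programmed. It states no precedence between its two rules, and its window cell does not carry over the timing beside it.

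The limits of the visible text also count. The schedule of assessments is not shown, so imaging at Week 8 is unconfirmed: SAP 10.1 speaks only of some parameters, and the by-visit volume summary in SAP 10.3 is a hint, not proof. SAP 17.3 cannot be read, so it cannot be said that the plan has no rule for a missing image.

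The size is also not study evidence. A 6-month denominator may overstate the shortfall against a final visit 12 weeks after treatment, while an image from before session 2 could have a lower ratio. Nothing in the documents settles r or k.

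**Conclusion.** The point holds as an error of specification with a probably small effect. The final-visit window in SAP 17.2 does not apply the Week 12/20 timing in its own row. It conflicts with the closest-to-target rule for any repeated CSQ or image. Taken literally, it lets an earlier volume image stand in for a missing final one. The last part depends on an earlier image existing. On the illustrative ratio of 0.8, the mean volume change would be understated by roughly 0.4% to 2% for 2 to 10 missing final images among 98. Few evaluable participants should lack a final image, since all have reported CSQ Item #1 at the final time point.

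Three stronger readings are not supported:

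- A reader might infer that Week 8 satisfaction answers enter the primary rate. SAP 6.3 prevents that, provided membership is judged by the scheduled Week 12 or 20 visit and not by the derived visit in 17.2.
- A reader might infer the opposite, that the primary endpoint cannot be touched at all. A repeated CSQ would meet the same conflict between latest and closest.
- A reader might infer a material bias in volume. That needs values of r and k for which the documents give no basis.

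The baseline difference is a wording point. The two definitions diverge only for assessments made on the treatment day before the first cycle, and the visible text does not show whether baseline images are taken then.

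**What to change.** In SAP 17.2:

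1. Replace the final-visit window with the assessment from the scheduled final visit: Week 12 after one session, Week 20 after two, within the +14 days already stated.
2. Keep closest-to-target as the only rule for repeats, and name the target day.
3. State that the Week 8 visit, and any assessment before the last session, is never used as final.
4. State that a missing final image is counted as missing, and report how many participants this affects.
5. Align the baseline definitions in 17.2 and 10.1.

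The evaluable definition in SAP 6.3 stays as it is, so nobody leaves the evaluable population. The cost is wording and programming specification, with no new data. The downside is that a few volume values may become missing.

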The count and percentage of participants with the same categories as the primary endpoint for CSQ Item #1 will be summarized and the 95% CIs for the percentages will be calculated.

Descriptive summary statistics of change in volume of fat from baseline will be provided by visit.

[REDACTED]

[REDACTED]

[REDACTED]

[REDACTED]

[REDACTED]

[REDACTED]

[REDACTED]

[REDACTED]

[REDACTED]

- █ [REDACTED]
- █ [REDACTED]
- █ [REDACTED]
- █ [REDACTED]
- █ [REDACTED]

[REDACTED]

[REDACTED]

[REDACTED]

[REDACTED]

[REDACTED]

11.1 **SAFETY ANALYSES**

The safety analyses will be based on the safety population.

11.2 **ADVERSE EVENTS**

Adverse events (AEs) will be collected throughout the study beginning with the first treatment visit. Adverse events will be coded by system organ class and preferred term using the *Medical Dictionary for Regulatory Activities*, version 22.0 or newer. AEs, AE severity, and causality are defined in the protocol (Section 11.1).

An AE will be considered a treatment-emergent (TEAE) if the AE began or worsened (increased in severity or became serious) on or after the treatment start date and time. An AE is considered an ADE if the AE with a reasonable possibility (Possible, Probable, or Causal relationship) that the device caused the event. An AE is considered a study procedure related AE if the AE with a reasonable possibility (Possible, Probable, or Causal relationship) that the procedure caused the event.

Overall summary of TEAEs, SAEs, ADEs, SADEs, study procedure related AEs, TEAEs leading to study discontinuation, and deaths will be presented as total and by treatment session. AEs/ADEs occurred on or after the date of treatment sessions 1 and before the date of treatment session 2 are counted for treatment session 1; AEs/ADEs occurred on or after the date of treatment sessions 2 are counted for treatment sessions 2.

The number and percentage of participants will be summarized by System Organ Class (SOC) and Preferred Term (PT), with or without by severity, as total and by treatment session as follows:

- TEAEs by SOC and PT
- TEAEs by SOC, PT, and severity
- ADEs by SOC and PT
- ADEs by SOC, PT, and severity
- Study Procedure Related AE by SOC and PT
- Treatment-emergent Serious AEs (SAEs) by SOC and PT
- Serious ADEs (SADEs) by SOC and PT
- TEAEs leading to study discontinuation by SOC and PT

The AE summary tables by SOC and PT will be presented with SOC in alphabetical order and in decreasing frequency within each SOC.

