If the causal relationship to the study treatment is missing for an AE that started on or after the date of the first study treatment, a causality of yes will be assigned. The imputed values for causal relationship to study treatment will be used for the incidence summary; the values will be shown as missing in the data listings.

17.7**MISSING DATE INFORMATION FOR ADVERSE EVENTS**

The following imputation rules only apply to cases in which the start date for AEs is incomplete (i.e., partly missing).

Missing month and day

- If the year of the incomplete start date is the same as the year of the first study treatment, the month and day of the first study treatment will be assigned to the missing fields

- If the year of the incomplete start date is before the year of the first study treatment, *December 31* will be assigned to the missing fields
- If the year of the incomplete start date is after the year of the first study treatment, *January 1* will be assigned to the missing fields

Missing month only

- If only the month is missing, the day will be treated as missing and both the month and the day will be replaced according to the above procedure

Missing day only

- If the month and year of the incomplete start date are the same as the month and year of the first study treatment, the day of the first study treatment will be assigned to the missing day
- If either the year of the incomplete start date is before the year of the first study treatment or if both years are the same, but the month of the incomplete start date is before the month of the first study treatment, the last day of the month will be assigned to the missing day
- If either the year of the incomplete start date is after the year of the date of the first study treatment or if both years are the same, but the month of the incomplete start date is after the month of the date of the first study treatment, the first day of the month will be assigned to the missing day

If the stop date is complete and the imputed start date as above is after the stop date, the start date will be imputed by the stop date.

If the start date is completely missing and the stop date is complete, the following algorithm will be used to impute the start date:

- If the stop date is after the date of the first study treatment, the date of the first study treatment will be assigned to the missing start date

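### AE start-date imputation uses only the first treatment, so some incompletely dated session 2 events are counted under session 1 in the by-session AE tables

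*SAP*

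**What the plan says.** SAP 17.7 gives these rules for an AE whose start date is incomplete:

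- **Month and day missing (or month only, which is handled the same way).** For an event in the calendar year of session 1, the SAP rule is that "the month and day of the first study treatment will be assigned to the missing fields". A later calendar year is a separate branch and takes 1 January of that later year.
- **Day only missing.** An event in the same month as session 1 takes the session 1 day. For any later month the SAP rule is that "the first day of the month will be assigned to the missing day".
- **Start wholly missing, with a known stop date later than session 1.** Here the SAP rule is that "the date of the first study treatment will be assigned to the missing start date".
- **The one correction for partly missing dates.** An imputed start that would fall later than a known stop is pulled back to that stop. This can only move a start earlier.

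None of these rules mentions the second session.

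SAP 11.2 uses the start date to choose a session. The overall summary, which ends with "TEAEs leading to study discontinuation, and deaths will be presented as total and by treatment session", divides events by onset. An event that begins once session 1 has taken place but "before the date of treatment session 2 are counted for treatment session 1". Later onsets, including any on the day of session 2 itself, go to session 2. The tables by system organ class and preferred term are split in the same way. SAP 12.1 repeats the by-session TEAE and ADE tables for Chinese participants, Asian participants, number of cycles, and country/site.

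**The concern.** The imputed date decides which session an event is charged to, but the imputation ignores the date that separates the sessions. First-treatment anchoring is enough to settle whether an event is treatment-emergent. It is not enough to settle which of two treatments the event followed.

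At stake is the allocation of events between sessions in prespecified safety tables. Elsewhere the SAP resolves missing AE information against the device: severity missing after first treatment becomes severe (17.5), and missing causality becomes related (17.6). The start-date rule does the same for treatment emergence, but for session 2 it can only take events away.

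**Working it through.** The documents state no figure on this point, so there is none to reproduce. The check applies the SAP 17.7 rules and then the SAP 11.2 split.

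**Direction.** Let T1 and T2 be the session dates and A the true onset, with A on or after T1. The imputed start S is one of T1, the 1st of A's month, 1 January of A's year, or the stop date where the correction applies. When a partial-date rule uses the 1st of the month or 1 January, that date is no later than A. T1 is no later than A by assumption. The correction only makes S earlier. So S ≤ A always, which gives two results:

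- If A < T2, then S < T2. No session 1 event moves to session 2.
- If A ≥ T2, S may still fall before T2. A session 2 event can move to session 1.

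**Worked example.** T1 = 10 Jan 2020; T2 = T1 + 56 days = 6 Mar 2020; A = 8 Mar 2020.

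| Missing | Imputed start | Counted under |
|---|---|---|
| Month and day | 10 Jan 2020 | session 1 |
| Day | 1 Mar 2020 | session 1 |
| Whole start, stop date known | 10 Jan 2020 | session 1 |

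**Events that stay in session 2.**

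- Onset 5 Apr 2020 with the day missing becomes 1 Apr 2020, after T2.
- With sessions on 10 Oct and 5 Dec 2019, an event in January 2020 known only by year becomes 1 Jan 2020, after T2.

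**A year-end variant that moves.** With sessions on 10 Dec 2019 and 4 Feb 2020, an event on 20 Feb 2020 known only by year becomes 1 Jan 2020 and is counted under session 1. This is a rarer form of the month-and-day-missing case.

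**Share moved.** Inputs from the documents: second session about 8 weeks after the first (Protocol 8.3), taken as 56 days; follow-up 12 weeks after the final session (SAP 4.0), taken as 84 days. Assumptions not in the documents: first treatments spread evenly over the 365 days of 2019, onset uniform within the window shown, and stop date 10 days after onset. All combinations were enumerated, and share moved = (events with S < T2) / (all true session 2 events).

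| Onset after session 2 | Month and day missing | Day missing | Start wholly missing |
|---|---|---|---|
| Within 12 weeks (365 × 84 = 30,660) | 27,090 = 88.4% | 5,397 = 17.6% | 30,660 = 100% |
| First 14 days (365 × 14 = 5,110) | 5,005 = 97.9% | 3,860 = 75.5% | 5,110 = 100% |
| First 3 days (365 × 3 = 1,095) | 1,089 = 99.5% | 1,023 = 93.4% | 1,095 = 100% |

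The same enumeration for session 1 events (365 × 56 = 20,440) moved none to session 2 under any pattern. No session 2 event was given a start before T1, so none lost treatment-emergent status.

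**Boundary.** The rule for a wholly missing start covers a stop date after the first treatment and one before it. A stop date equal to the first-treatment date has no rule.

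**The case against.** The strongest reply is that this will rarely matter. AEs are solicited at every visit (Protocol 9.2.1), the date of first occurrence is a required CRF item, and missing data are queried (Protocol 12.3). In a study of at most 20 weeks, dates with only the year, or no start date at all, should be uncommon. The mild-to-moderate transient effects listed in Protocol 5.2.1.2 are generally not AEs. The protocol's safety endpoint is overall AE frequency, and Protocol Section 10 says no hypothesis is tested. All of this stands and limits the point to a clarification.

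Three stronger readings are tempting, and the documents do not support them:

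- **That every partially dated session 2 event moves, or every year-only event when both sessions fall in one year.** The two examples above that stay in session 2 show otherwise.
- **That about 29 in 30 day-missing events are misplaced.** That ratio is roughly the share of session 2 dates not on the 1st of a month. It applies only within the session 2 calendar month, and the events there include true session 1 events that are correctly placed.
- **That session 2 will look safer than it is.** SAP 11.2 allocates by onset date alone, so a late effect of session 1 that begins after session 2 is charged to session 2. Paradoxical hyperplasia, described in Protocol 5.2.1.2 as developing 2 to 5 months after treatment, is an example. That error runs the other way, so the net direction for the tables is not established.

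What the reply does not remove is that the rule, followed exactly, misplaces identifiable events and errs in one direction only.

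**Conclusion.** The point holds in limited form, as a minor repair. In participants with two sessions, SAP 17.7 combined with SAP 11.2 puts a true session 2 event under session 1 when:

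- (a) only the day is missing, the event is in session 2's calendar month, and session 2 was not on the 1st;
- (b) month and day are missing and the event year is the first-treatment year (plus the year-end variant shown above); or
- (c) the start is wholly missing and the stop date is on or after session 2.

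The imputation error is one-directional. It is confined to the by-session AE and ADE tables and their subgroup versions. The percentages apply only to incompletely dated session 2 events and depend on the assumed onset window, most strongly in the day-missing case. The documents do not give the number of such events, so the absolute effect cannot be stated and is probably small.

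**What to change.** Keep the present rules for treatment-emergent status. Add to SAP 17.7 a session-allocation rule for participants with two sessions:

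1. If only the day is missing and the month and year are those of session 2, impute the session 2 date, unless the stop date or other records (for example, the visit at which the event was first reported) show that it began earlier.
2. If month and day are missing, or the start is wholly missing, allocate by the stop date and other records where these place onset before or after session 2. Where they do not, keep the event in the total and show it as 'session undetermined' in the by-session tables. Allocating such events to session 2 can be a stated sensitivity analysis. It should not be the main rule, because sending every year-only event to session 2 would reverse the error.
3. In the rule for a wholly missing start, change 'before' to 'on or before' the date of the first study treatment.

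The cost is a few sentences before database lock, plus one extra table row. Treatment dates are already used: SAP 17.8.2 anchors medication stop dates to the last treatment, and 17.4 gives a fallback if that date is missing. The downside is that a few day-missing events that truly began before session 2 may be attributed to it.
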